9.2.3 Other Endpoints

The survey includes HCP characteristics and other outcomes that may be treated as covariates for data analysis. These questions are described in Table 9-2.

Table 9-2 Other outcomes collected in the survey

Data collected	Variable type	Operation definition/derivation
Years practicing as a physician	Categorical	< 5 years, 5 to <10 years, 10 to <15 years, ≥15 years, prefer not to answer
Number of patients for which the HCP has prescribed ENJAYMO™	Categorical	None, <5 patients, 5-10 patients, >10 patients, prefer not to answer
HCP confirmed distribution of the ENJAYMO™ Patient Guide	Categorical	Yes, no, I don’t know/am not sure
HCP confirmed vaccination status in the patient most recently prescribed ENJAYMO™	Categorical	Yes, no, I don’t know/am not sure
Vaccines HCP checked in the patient most recently prescribed ENJAYMO™	Categorical	Meningococcal conjugate vaccine(s), meningococcal serogroup B vaccine(s), pneumococcal vaccine(s), Other (please specify), I don’t know/am not sure
Vaccines up-to-date in the patient most recently prescribed ENJAYMO™	Categorical	Yes, no, I don’t know/am not sure
HCP administered or prescribed vaccines to the patient most recently prescribed ENJAYMO™	Categorical	Yes, no, I don’t know/am not sure
Reason HCP did not provide vaccines to the patient most recently prescribed ENJAYMO™	Categorical	The patient refused vaccination, the patient received vaccination elsewhere, I don’t know/am not sure
Timing of vaccination relative to starting ENJAYMO™ in the patient most recently prescribed ENJAYMO™	Categorical	At the same time ENJAYMO™ treatment was started, less than two weeks before ENJAYMO™ treatment was started, two weeks before ENJAYMO™ treatment was started, I don’t know/am not sure

HCP counselled the patient most recently prescribed ENJAYMO™ to seek immediate medical attention if they experience symptoms of serious infection	Categorical	Yes, no, I don't know/am not sure
Investigator in ENJAYMO™ clinical trial	Categorical	Yes, no, prefer not to answer
Involvement with CADENCE patient registry	Categorical	Yes, no, prefer not to answer

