9.2.2 Secondary

Secondary endpoint questions include:

- The distribution of HCPs' reported levels of receipt and reading of the ENJAYMO™ Physician's Guide,
- HCPs' knowledge levels for each question regarding the information included in the ENJAYMO™ Physician's Guide (i.e., all questions relating to all domains), assessed as the percentages of HCPs with correct responses to each question,
- The distribution of HCP's reported levels of dissemination of the ENJAYMO™ Patient Guide to patients treated with ENJAYMO™ (questions asked to ENJAYMO™ prescribers only),
- The distribution of HCPs' responses regarding their experience with patients' receptivity to vaccination (questions asked to ENJAYMO™ prescribers only),
- Implementation of vaccination (questions asked to ENJAYMO prescribers only), and
- The distribution of responses regarding the primary source(s) from which HCPs learned about the information included in the ENJAYMO™ Physician's Guide.

Table 9-1 Outcomes/endpoints collected in the survey

Study Objective Domains Assessed	Corresponding variable	Operational definition/derivation "Calculated as the percentage of HCPs who"*
HCPs' knowledge of the indication for ENJAYMO™ treatment in adult patients with CAD (not patients with cold agglutinin syndrome)	Knowledge that ENJAYMO™ is indicated for the treatment of hemolytic anemia in CAD patients	For question 3: "Checked" hemolytic anemia
	Knowledge that ENJAYMO™ is not indicated for the treatment of jaundice	For question 3: "Not checked" jaundice
	Knowledge that ENJAYMO™ is not indicated for the treatment of cardiac arrhythmia	For question 3: "Not checked" cardiac arrhythmia
	Knowledge that ENJAYMO™ is not indicated for the treatment of nausea and vomiting	For question 3: "Not checked" nausea and vomiting
	Knowledge that ENJAYMO™ is not indicated for the treatment of patients with cold agglutinin syndrome	For question 3: "Not checked" indicated for patients with cold agglutinin syndrome

Study Objective Domains Assessed	Corresponding variable	Operational definition/derivation “Calculated as the percentage of HCPs who”*
HCPs’ knowledge of important potential risks of serious infections from encapsulated bacteria	Knowledge that ENJAYMO™ should only be prescribed to patients who have received appropriate vaccinations, especially against encapsulated bacteria	Checked “true” to question 4

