9.9.1.2 Statistical Methods

Data analysis will be performed by ICON qualified personnel in accordance with ICON's SOPs for statistical analysis and programming. All analyses will be performed using appropriate statistical software (e.g., SAS[®] Version 9.0 or later). A report summarising the results of the survey will be developed.

The primary criteria is the composite knowledge level for the core question set. The composite will be an opportunity/denominator based weighted percentage of HCPs who have answered each item correctly (if at least 30 HCPs have completed the item).

Other criteria include measures of receipt and reading of the ENJAYMO™ Physician's Guide, knowledge levels for each question regarding the information included in the ENJAYMO™ Physician's Guide (i.e., all questions relating to all domains), assessed as the percentages of HCPs with correct responses to each question, the distribution of HCPs' responses regarding their experience with patients' receptivity to vaccination and the implementation of vaccination (date of vaccination versus treatment start, if the prescriber administered the vaccinations), and the distribution of responses regarding the primary source(s) from which HCPs learned about the information included in the ENJAYMO™ Physician's Guide.

Descriptive data analyses will be conducted for all primary and secondary objectives. Descriptive statistics for continuous data will include N, means, and standard deviations. Results for some continuous variables may include ranges (minimums and maximums) and medians as well. Categorical data will be summarised using frequency counts and percentages. Knowledge levels will be calculated with 95% 2-sided CI. Knowledge levels will also be stratified by items with potential to confound the knowledge level (e.g., country, specialty, reads/uses vs. did not read/does not use the ENJAYMO™ Physician's Guide,

prescribing status). Missing data will be reported, but no replacement or imputation will be performed.

For each primary endpoint, the weighted average percentage of HCPs who answered the core question set correctly will be estimated and assessed against the 80% (\pm 95% CI) target (if the number of HCPs who answered the item is at least 30).

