[ON-LINE SURVEY - PROGRAMMER: RANDOMISE THE ORDER OF THE FIRST 5 RESPONSE OPTIONS]

HCP CHARACTERISTICS

[Preamble 2]: Below are 7 additional questions to help us combine your answers with other answers we have received, and to help us interpret the survey results. **THERE ARE NO CORRECT RESPONSES TO QUESTIONS 10, 11, 19, and 20. DISPLAY QUESTIONS 12-18 ON THE SAME PAGE.**

10. Approximately how many years have you been practicing as a physician?
- <5 years
 - 5 to <10 years
 - 10 to <15 years
 - ≥15 years
 - Prefer not to answer
11. Approximately how many patients have you treated with ENJAYMO™ (sutimlimab)?
- None → **PROCEED TO QUESTION 20**
 - < 5 patients → **PROCEED TO QUESTION 12**
 - 5-10 patients → **PROCEED TO QUESTION 12**
 - >10 patients → **PROCEED TO QUESTION 12**
 - Prefer not to answer → **PROCEED TO QUESTION 20**
12. For the most recent patient you prescribed ENJAYMO™ (sutimlimab), did you provide the patient with a copy of the ENJAYMO™ Patient Guide?
- Yes → **PROCEED TO QUESTION 13**
 - No → **PROCEED TO QUESTION 13**
 - I don't know/am not sure → **PROCEED TO QUESTION 13**
13. For the most recent patient you prescribed ENJAYMO™ (sutimlimab), did you confirm that their vaccination status is up-to-date according to local guidelines or recommendations for patients with persistent complement deficiencies?
- Yes → **PROCEED TO QUESTION 14**
 - No → **PROCEED TO QUESTION 19**
 - I don't know/am not sure → **PROCEED TO QUESTION 19**

14. For the most recent patient you prescribed ENJAYMO™ (sutimlimab), which vaccines did you check the status of? Please select all that apply.
- Meningococcal conjugate vaccine(s)
 - Meningococcal serogroup B vaccine(s)
 - Pneumococcal vaccine(s)
 - Other (not listed above); specify: _____
 - I don't know/am not sure
15. For the most recent patient you prescribed ENJAYMO™ (sutimlimab), was the patient up-to-date on their vaccinations?
- Yes → **PROCEED TO QUESTION 19**
 - No → **PROCEED TO QUESTION 16**
 - I don't know/am not sure → **PROCEED TO QUESTION 19**
16. For the most recent patient you prescribed ENJAYMO™ (sutimlimab), did you administer or prescribe vaccines to the patient?
- Yes → **PROCEED TO QUESTION 18**
 - No → **PROCEED TO QUESTION 17**
 - I don't know/am not sure → **PROCEED TO QUESTION 19**
17. For the most recent patient you prescribed ENJAYMO™ (sutimlimab), what was the reason you did not provide vaccination?
- The patient refused vaccination → **PROCEED TO QUESTION 19**

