 - The patient received vaccination elsewhere → **PROCEED TO QUESTION 18**
 - I don't know/am not sure → **PROCEED TO QUESTION 19**
18. For the most recent patient you prescribed ENJAYMO™ (sutimlimab), when were vaccinations administered relative to starting of ENJAYMO™ (sutimlimab)?
- At the same time ENJAYMO™ treatment was started
 - Less than two weeks before ENJAYMO™ treatment was started
 - Two weeks before ENJAYMO™ treatment was started
 - I don't know/am not sure

19. For the most recent patient you prescribed ENJAYMO™ (sutimlimab), did you counsel them to seek immediate medical attention if they experience symptoms associated with risks of serious infections or meningococcal infections associated with ENJAYMO™ (sutimlimab)?
- Yes
 - No
 - I don't know/am not sure
20. Have you previously participated as an investigator of a clinical trial assessing ENJAYMO™ (sutimlimab) treatment?
- Yes
 - No
 - Prefer not to answer
21. Are you involved in the CADENCE patient registry for Cold Agglutinin Disease and Cold Agglutinin Syndrome?
- Yes
 - No
 - Prefer not to answer

CLOSING

Thank you for taking the time to complete this survey.

You may now close this browser.

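### The vaccination items lack needed answer options and Question 13 is ambiguous, so implementation of vaccination cannot be measured as described

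*Protocol*

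**What the plan says.** Section 9.2.2 lists implementation of vaccination as a secondary endpoint for prescribers only. Section 9.9.1.2 describes it as "implementation of vaccination (date of vaccination versus treatment start, if the prescriber administered the vaccinations", and Section 9.11 repeats that description.

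The data come from Questions 13 to 18 in Annex 3, tabulated in Table 9-2 (Section 9.2.3):

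- **Question 13** asks, for the most recent patient, "did you confirm that their vaccination status is up-to-date according to local guidelines or recommendations for patients with persistent complement deficiencies". A 'no' or 'don't know' goes straight to Question 19.
- **Question 15** asks whether the patient was up to date. Only 'no' leads on to Question 16.
- **Question 16** asks whether the HCP gave or prescribed vaccines. 'Yes' leads to Question 18 and 'no' to Question 17.
- **Question 17** asks why not. Its answers are "The patient refused vaccination, the patient received vaccination elsewhere" and don't know.
- **Question 18** asks "when were vaccinations administered relative to starting of ENJAYMO™ (sutimlimab". Its answers are "At the same time ENJAYMO™ treatment was started, less than two weeks before ENJAYMO™ treatment was started, two weeks before ENJAYMO™ treatment was started" and don't know.

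Section 9.7 expects possibly 10 prescribers among 50 HCPs. The per-question denominator rule in Section 9.9.1.1 is stated for knowledge levels only.

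**The concern.** A timing endpoint needs a timing item that can hold every possible timing. Question 18 cannot record vaccination after treatment began. That is a departure this survey would want to see, since Question 4 marks as correct that the product should go only to patients already appropriately vaccinated. It also has no place for vaccination well ahead of treatment. Such cases must be put in a wrong category or in don't know.

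Question 17 matters beyond its own item. Its refusal option is the only answer in Annex 3 that bears on the separate secondary endpoint of patients' receptivity to vaccination. Any unlisted reason either distorts that endpoint or is lost.

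At Question 13, an HCP who checked, found the patient not up to date and then vaccinated can truthfully answer 'no'. That vaccination is then never recorded.

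**Working it through.** **1. The plan's own precision figure.** The simple asymptotic half-width is 1.96 × √(p(1−p)/n). At n = 50 and p = 0.80 this is 1.96 × √(0.16/50) = 11.1 points, which agrees with Section 9.7. That figure is for the primary endpoint; none is given for the vaccination items. If all 10 expected prescribers answered an item, the half-width would be 1.96 × √(0.16/10) = 24.8 points at 80% and 1.96 × √(0.25/10) = 31.0 points at 50%.

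**2. Timing answers against possible timings.**

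| Vaccination relative to treatment start | Option in Question 18 and Table 9-2 |
|---|---|
| More than two weeks before | none |
| Two weeks before | yes |
| Less than two weeks before | yes |
| Same time | yes |
| After | none |

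Two of the five possible timings have no category, and there is no 'other'.

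**3. Reasons.** Question 17 offers two substantive reasons and don't know, with no 'other' and no free text. Question 14 does have a free-text 'other'.

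**4. Routes through the skips.** Following the Annex 3 instructions gives six routes:

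- 12, 13, 19
- 12 to 15, 19
- 12 to 16, 19
- 12 to 16, 18, 19
- 12 to 17, 19
- 12 to 19 in full

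Timing is therefore asked only after 'yes' at Question 13 and 'no' at Question 15, followed either by 'yes' at Question 16 or by 'no' at Question 16 with vaccination elsewhere at Question 17. The first route mixes HCPs who did not check, HCPs who checked and found the patient not up to date, and HCPs who are unsure.

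**5. How many reach the later items.** Let c be the number answering 'yes' at Question 13, u the share of those whose patient is up to date, and a the share of the remainder vaccinated by the HCP or elsewhere. Then c(1−u) reach Question 16 and c(1−u)a reach Question 18. Section 9.7 gives 10 prescribers; c, u and a are assumptions.

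- c = 8, u = 0.50: 8 × 0.50 = 4 reach Question 16, and 0 to 4 reach Question 18.
- c = 8, u = 0.75: 8 × 0.25 = 2 reach Question 16, and 0 to 2 reach Question 18.

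**6. Direction of error.** Take c = 8 and u = 0.75, so that 6 patients are up to date and 2 are not. Suppose each item is reported only on those who reached it.

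- Question 15 reads 6/8 = 75%, against 6/10 = 60% of all prescribers with a patient documented as up to date.
- Question 16 reads 2/2 = 100% if the HCP vaccinated both remaining patients, against (6+2)/10 = 80% documented over all prescribers.
- Question 16 reads 0/2 = 0% if neither was vaccinated, although 6/10 = 60% are documented as up to date.

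The item-level figure can lie on either side of the all-prescriber figure. If all 10 say 'yes' at Question 13, the gap at Question 15 disappears.

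**The case against.** A reader might infer that the endpoint will be overstated because the skips drop those who did not implement. The protocol does not support that. It fixes no numerator or denominator for these items, and a SAP may do so. Question 13 is put to every prescriber, and Table 9-2 keeps its 'no' and 'don't know' categories, so those HCPs stay visible. The skips also remove implementers, because an up-to-date patient at Question 15 bypasses Questions 16 to 18. An all-prescriber summary can already be built from Questions 13, 15, 16 and 17.

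Three other strong readings also go too far:

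- Not timing patients who were already up to date is largely within the stated scope, because Sections 9.9.1.2 and 9.11 tie timing to vaccination by the prescriber.
- These are not the only behavioural outcomes: Question 12 covers handing over the Patient Guide and Question 19 covers counselling.
- Sending a 'no' at Question 13 to Question 16 would be no remedy. It bypasses Question 15 and leaves the ambiguous wording in place.

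It is also fair to say that the endpoint is descriptive, that about 10 prescribers are expected, and that Section 9.11 already warns of few responses. That warning attributes the shortage to the mix of prescribers and non-prescribers, however, and not to the routing.

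None of this reaches the missing answers or the double meaning of Question 13. A SAP can define denominators, but it cannot recover answers that were never offered. Section 9.8 bars respondents from revising earlier answers, and Section 9.1.1 would use the same survey in a second wave.

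**Conclusion.** The point holds as a measurement defect in a secondary endpoint. Vaccination after treatment start, or more than two weeks before it, cannot be recorded. Reasons outside two options cannot be recorded. A 'no' at Question 13 has two meanings, and both routes lose any later vaccination. No direction of bias can be claimed.

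Under the assumptions in the working, timing would rest on 0 to 4 HCPs. The number of cases that would fall outside the answer lists is not knowable from the protocol. The conclusion assumes that the Annex 3 skips are enforced as written, although Annex 3 also asks for Questions 12 to 18 to appear on one page. The primary endpoint is untouched.

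**What to change.** In Annex 3 and Table 9-2:

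1. Add two options to Question 18: more than two weeks before treatment was started, and after treatment was started.
2. Add 'Other, specify' to Question 17.
3. Reword Question 13 to ask only whether vaccination status was checked, leaving up-to-date status to Question 15. HCPs who checked and found the patient not up to date then continue through Questions 15 to 18.
4. Summarise implementation over all prescribers reaching Question 12, with the count on each route shown.

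These are answer categories only; no clinical timing rule is proposed or implied.

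The cost is a few lines of text in each survey language, with the independent proofreading and signed affiliate review that Section 9.1.2 requires. Section 6 plans data collection from Q2 2024, dependent on launch, and the title page dates the last protocol version 05 June 2024, so collection may already have begun. If it has, answers to these items before and after the change must be reported separately and not pooled across waves.

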9.3 Study Design

This is a multinational, non-interventional, cross-sectional survey study to evaluate the effectiveness of the ENJAYMO™ Physician's Guide among EEA-based HCPs.

The current study is planned to be conducted among HCPs in countries in the EEA where the product is expected to be commercially available for at least 6 months. The survey will be launched no sooner than 6 months, and no longer than 18 months, after the ENJAYMO™ Physician's Guide has been disseminated in each participating country. Countries may include Austria, Germany, Italy, and the Netherlands. A convenience sample of HCPs will be recruited from the target population of HCPs who treat patients with CAD and may prescribe ENJAYMO™ in these countries.

The survey is anticipated to be open between 3 to 6 months per country per wave. Depending on response rates, follow-up reminders will be sent to non-respondents to endeavor to achieve the target sample size, and the medical scientific liaison team of Sanofi may also be involved in some countries to advocate for the participation in the survey through their personal contacts with HCPs already contacted via e-mail. In the event that less than 30 completed surveys are achieved in the first wave of the study, a second wave of the same survey will be triggered.

Data will be collected by web-based electronic data capture. Information collected will include the receipt and reading of the ENJAYMO™ Physician's Guide, knowledge of the key information included in the ENJAYMO™ Physician's Guide, the impact of the ENJAYMO™ Physician's Guide on clinical action, and HCP characteristics.

All data will be maintained in compliance with local regulations. Results will be analyzed using SAS. Results will be summarized in tables and figures (as applicable). A statistical analysis plan will be developed to describe the planned statistical analyses in detail and finalized prior to the end of data collection. A final study report will be prepared.

9.4 Study Population

Generally, it is preferable to conduct surveys to assess HCPs' knowledge and awareness of product-specific aRMM amongst HCPs actually engaging with the product (e.g., prescribers or HCPs managing care for patients receiving the product). However, since ENJAYMO™ is used to treat CAD, a rare disease, and will also be a newly authorised product where reimbursement applications and decisions will be ongoing, the number of prescribers may be low and therefore it may be challenging to identify a sufficient number of HCP prescribers to obtain robust and precise estimates of knowledge level. This survey will therefore be open to any HCP who was targeted to receive the aRMM for the product and is likely to prescribe (even though may not have yet prescribed) ENJAYMO™.

9.4.1 Selection of Study Population

To determine HCPs' eligibility, screening questions will be presented in the on-line survey in the order presented in [Sections 9.4.2](#) followed by [9.4.3](#).

9.4.2 Inclusion Criteria

HCPs will be eligible for this survey if they meet the following criteria:

1. Prescribers, and potential prescribers, of ENJAYMO™.
2. Provides permission to share their responses in aggregate with EMA or national competent authorities, if requested.

9.4.3 Exclusion Criteria

HCPs will not be eligible for this survey if they meet the following criteria:

1. Is or has been a direct employee of Sanofi, the EMA, or the study vendor (ICON plc) within the last five years.

9.5 Treatments and Evaluation

No tests or reference treatments are evaluated in this cross-sectional survey study.

9.5.1 Discontinuation Criteria

Participation in this survey is voluntary and will not affect HCPs' ability to prescribe ENJAYMO™. HCPs may withdraw from the study for any reason, at any time, without penalty or prejudice. If requested by an HCP, their survey responses will be removed from the analysis database and not used in the final study report.

9.6 Variables

The survey questionnaire includes the following:

- Screening questions to determine eligibility for survey participation,

- Questions regarding the receipt, reading, and use of the ENJAYMO™ Physician's Guide,
- Questions regarding the dissemination of the ENJAYMO™ Patient Guide,
- Questions to assess knowledge of the core messages included in ENJAYMO™ Physician's Guide,
- Questions to assess HCPs' experience with patients' receptivity to vaccination (asked of HCPs who have prescribed ENJAYMO™ only), and
- Brief questions on HCP characteristics.

The main survey questions are described in [Sections 9.2.1](#) and [9.2.2](#) and Table 9-1 and 9-2.

9.7 Study Size

A sample of 50 completed surveys is targeted for this study, with possibly 10 of the HCPs having actually prescribed ENJAYMO™ (this number depends on uptake of ENJAYMO™ and is very difficult to predict). Although reasonable efforts will be made to reach the target, the actual sample size will depend on actual prescribing of ENJAYMO™ as well as HCPs' willingness to participate. The sample size was determined based on both feasibility and statistical considerations, giving the rarity of CAD and therefore anticipated low number of actual ENJAYMO™ prescribers.

A recent meta-analysis of data from 23 HCP surveys found the proportions of HCPs who completed a survey among those invited ranged from 0.5% to 26.0%, with a pooled estimated proportion of 2.1% (95% confidence interval [CI]: 2.1-2.2) based on a fixed effects model, or 4.7% (95% CI: 3.0-6.6) based on a random effects model(4). Based on this plus the ICON's anecdotal experience with similar surveys, this survey estimates that a response rate of 5% is achievable. Based on this estimated response rate, at least 1,000 HCPs may need to be contacted to obtain 50 completed surveys.

Error! Reference source not found. below provides the precision and 2-sided 95% CI for different assumptions regarding levels of knowledge and number of completed surveys for this study. The primary evaluation criteria is the composite weighted average knowledge levels for the core question set. With a response from 50 HCPs and an observed knowledge level of 80%, the true value would be estimated to lie within the margin of 68.9-91.1% (i.e. with a precision of 11.1%).

Table 9-3: Precision and 95% Confidence Intervals for Various Combinations of Sample Size and Knowledge Levels

Sample Size	Probable Respondent Knowledge Levels							
	60%		70%		80%		90%	
	Precision (%)	95% CI	Precision (%)	95% CI	Precision (%)	95% CI	Precision (%)	95% CI
25	19.2	40.8, 79.2	18.0	52.0, 88.0	15.7	64.3, 95.7	10.9	78.2, 100.0
50	13.6	46.4, 73.6	12.7	57.3, 82.7	11.1	68.9, 91.1	8.3	81.7, 98.3
75	11.1	48.9, 71.1	10.4	59.6, 80.4	9.1	70.9, 89.1	6.8	83.2, 96.8
100	9.6	50.4, 69.6	9.0	61.0, 79.0	7.8	72.2, 87.8	5.9	84.1, 95.9

Note: Calculated using PASS 12 software,* confidence intervals for 1 proportion, simple asymptotic formula.

* Hintze, J. (2014). PASS 12. NCSS, LLC. Kaysville, Utah, USA. www.ncss.com.

